3.2 IRB Approval

Local IRB/REB approval of this study must be obtained by a site prior to enrolling patients. Sites must submit IRB/REB approvals to the NCI's Cancer Trials Support Unit (CTSU) Regulatory Office and allow 3 business days for processing. The submission must include a fax coversheet (or optional CTSU IRB Transmittal Sheet) and the IRB approval document(s). The CTSU IRB Certification Form may be submitted in lieu of the signed IRB approval letter. All CTSU forms can be located on the CTSU web page (www.ctsu.org). Any other regulatory documents needed for access to the study enrollment screens will be listed for the study on the CTSU Member's Website under the RSS Tab.

Submitting Regulatory Documents:

Submit required forms and documents to the CTSU Regulatory Office, where they will be entered and tracked in the CTSU RSS.

ONLINE: www.ctsu.org (members' section) → Regulatory Submission Portal
EMAIL: [contact] (for regulatory document submission only)

[contact]

MAIL: CTSU Regulatory Office
[name]
[name]

When a site has a pending patient enrollment within the next 24 hours, this is considered a "Time of Need" registration. For Time of Need registrations, in addition to marking your submissions as 'URGENT' and faxing the regulatory documents, call the CTSU Regulatory Helpdesk at: [name]. For general (non-regulatory) questions, call the CTSU General Helpdesk at: [name].

3.3 Patient Registration

Prior to enrollment on study, all patients must be assigned a COG patient ID number. This number is obtained via the COG Registry system once authorization for the release of protected health information (PHI) has been obtained.

3.4 Reservation and Contact Requirements

Before enrolling a patient on study, a reservation must be made through the OPEN website and the Study Chair or Vice Chair should be notified. (The patient will need a COG patient ID number in order to obtain a reservation.) Patients must be enrolled within 7 calendar days of making a reservation.

Reservations may be obtained 24-hours a day through the OPEN website.

3.5 Informed Consent/Assent

The investigational nature and objectives of the trial, the procedures and treatments involved and their attendant risks and discomforts, and potential alternative

therapies will be carefully explained to the patient or the patient's parents or guardian if the patient is a child, and a signed informed consent and assent will be obtained according to institutional guidelines.

3.6 Screening Procedures

Diagnostic or laboratory studies performed exclusively to determine eligibility for this trial must only be done after obtaining written informed consent. This can be accomplished through one of the following mechanisms: a) the COG screening protocol, b) an IRB-approved institutional screening protocol or c) the study-specific protocol. Documentation of the informed consent for screening will be maintained in the patient's research chart. Studies or procedures that were performed for clinical indications (not exclusively to determine eligibility) may be used for baseline values even if the studies were done before informed consent was obtained.

3.7 Eligibility Checklist

Before the patient can be enrolled, the responsible institutional investigator must sign and date the completed eligibility checklist. A signed copy of the checklist will be uploaded into RAVE immediately following enrollment.

3.8 Institutional Pathology Report

Because DIPGs are often not biopsied, enrollment of patients with typical-appearing DIPG (see [Section 4.1.2](#)) without an institutional pathology report is allowed. For patients with brainstem tumors not considered typical DIPG as defined in [Section 4.1.2](#), they will only be eligible if their tumors are biopsied and meet the eligibility criteria as defined in [Section 4.1.2](#). Immediately following enrollment, the institutional pathology report for the diagnosis under which the patient is being enrolled must be uploaded into RAVE. The report must include the associated study number and COG patient registration and accession numbers. Personal identifiers, including the patient's name and initials must be removed from the institutional pathology report prior to submission.

3.9 Study Enrollment

Patients may be enrolled on the study once all eligibility requirements for the study have been met. Patients who give informed consent for the protocol in order to undergo screening for eligibility are not considered enrolled and should not be enrolled until the screening is completed and they are determined to meet all eligibility criteria. Study enrollment is accomplished by going to the CTSU OPEN (Oncology Patient Enrollment Network) <https://open.ctsu.org/open/>. For questions, please contact the COG Study Research Coordinator, or the CTSU OPEN helpdesk at <https://www.ctsu.org/CTSUCContact.aspx>. Patients must be enrolled before treatment begins. The date protocol therapy is projected to start must be no later than five (5) calendar days after the date of study enrollment. **Patients must not receive any protocol therapy prior to enrollment.**

3.10 Dose Assignment

The dose level will be assigned via OPEN at the time of study enrollment.

4.0 PATIENT ELIGIBILITY

All clinical and laboratory studies to determine eligibility must be performed within 7 days prior to enrollment unless otherwise indicated. Laboratory values used to assess eligibility must be no older than seven (7) days at the start of chemotherapy. The start of chemotherapy is defined as the initiation of treatment with AZD1775 (MK-1775). The start of protocol therapy is defined as the initiation of radiation therapy. Laboratory tests need **not** be repeated if chemotherapy starts **within** seven (7) days of obtaining labs to assess eligibility. If a post-enrollment lab value is outside the limits of eligibility, or laboratory values are older than 7 days, then the following laboratory evaluations must be re-checked within 48 hours prior to initiating chemotherapy: CBC with differential, bilirubin, ALT (SGPT) and serum creatinine. If the recheck is outside the limits of eligibility, the patient may not receive chemotherapy and will be considered off protocol therapy. Imaging studies must be obtained within 14 days prior to start of chemotherapy (repeat the tumor imaging if necessary).

Important note: The eligibility criteria listed below are interpreted literally and cannot be waived (per COG policy posted 5/11/01). All clinical and laboratory data required for determining eligibility of a patient enrolled on this trial must be available in the patient's medical or research record which will serve as the source document for verification at the time of audit.

4.1 Inclusion Criteria

4.1.1 Age: Patients must be $>$ than 36 months and \leq 21 years of age at the time of study enrollment. The first patient enrolled on study must be \geq 7 years of age. Pending results of PK analysis, the study will open to children of ages 3-21 years of age.

4.1.2 Diagnosis: Patients with newly diagnosed DIPGs, defined as tumors with a pontine epicenter and diffuse involvement of the pons, are eligible without histologic confirmation.

Patients with brainstem tumors that do not meet these criteria or are not considered to be typical intrinsic pontine gliomas will only be eligible if the tumors are biopsied and proven to be an anaplastic astrocytoma, glioblastoma, gliosarcoma, diffuse midline glioma with histone H3 K27M mutation, or anaplastic mixed glioma. Patients with pilocytic astrocytoma, fibrillary astrocytoma, gangliogliomas, or other mixed gliomas without anaplasia are not eligible.

Patients with disseminated disease are not eligible, and MRI of spine must be performed if disseminated disease is suspected by the treating physician.

Enrollment must be no later than 28 days after the date of radiographic diagnosis or surgery, whichever is the later date.

4.1.3 Body Surface Area: Patients must have a body surface area $\geq 0.35 \text{ m}^2$ at the time of study enrollment.

4.1.4 Performance Level: Karnofsky $\geq 50\%$ for patients > 16 years of age and Lansky ≥ 50 for patients ≤ 16 years of age (See [Appendix I](#)). Patients who are unable to walk because of paralysis, but who are up in a wheelchair, will be considered ambulatory for the purpose of assessing the performance score.

4.1.5 Prior Therapy

Patients must not have received any prior anti-cancer therapy such as chemotherapy, radiation therapy, immunotherapy or bone marrow transplant for the treatment of DIPG. Prior dexamethasone and/or surgery are allowed.

4.1.6 Organ Function Requirements

4.1.6.1 Adequate Bone Marrow Function Defined as:

- Peripheral absolute neutrophil count (ANC) $\geq 1000/\text{mm}^3$
- Platelet count $\geq 100,000/\text{mm}^3$ (transfusion independent, defined as not receiving platelet transfusions for at least 7 days prior to enrollment).

4.1.6.2 Adequate Renal Function Defined as:

- Creatinine clearance or radioisotope GFR $\geq 70\text{mL/min}/1.73\text{m}^2$ or
- A serum creatinine based on age/gender as follows:

Age	Maximum Serum Creatinine (mg/dL)	
	Male	Female
3 to < 6 years	0.8	0.8
6 to < 10 years	1	1
10 to < 13 years	1.2	1.2
13 to < 16 years	1.5	1.4
≥ 16 years	1.7	1.4

The threshold creatinine values in this table were derived from the Schwartz formula for estimating GFR utilizing child length and stature data published by the CDC.²³

4.1.6.3 Adequate Liver Function Defined as:

- Bilirubin (sum of conjugated + unconjugated) $\leq 1.5 \times$ upper limit of normal (ULN) for age.
- SGPT (ALT) $\leq 3 \times$ ULN = 135 U/L. For the purpose of this study, the ULN for SGPT is 45 U/L.
- SGOT (AST) $\leq 3 \times$ ULN = 150 U/L. For the purpose of this study, the ULN for SGOT is 50 U/L.
- Serum albumin ≥ 2 g/dL.

4.1.6.4 Adequate Neurologic Function Defined as:

- Patients with seizure disorder may be enrolled if on non-enzyme inducing anticonvulsants and well controlled. See [Appendix II](#) for a list of recommended non-enzyme inducing anticonvulsants

THIS PROTOCOL IS FOR RESEARCH PURPOSES ONLY, SEE PAGE 1 FOR USAGE POLICY

- Nervous system disorders (CTCAE v5) resulting from prior therapy must be \leq Grade 2 with the exception of tendon reflex (DTR). Any grade of DTR is eligible.

4.1.6.5 Adequate Cardiac Function Defined as:

- $QTc \leq 480$ msec

4.1.6.6 Informed Consent: All patients and/or their parents or legally authorized representatives must sign a written informed consent. Assent, when appropriate, will be obtained according to institutional guidelines.

4.2 Exclusion Criteria

4.2.1 Pregnancy, Breast-Feeding, and Contraception

- a. Pregnant or breast-feeding women may not be entered on this study as there is yet no available information regarding human fetal or teratogenic toxicities. Pregnancy tests must be obtained in girls who are post-menarchal. Negative serum or urine pregnancy test within 3 days prior to enrollment.
- b. Males or females of reproductive potential may not participate unless they have agreed to use an effective contraceptive methods as follows: fertile females of childbearing potential who agree to use adequate contraceptive measures from 2 weeks prior to the study and until 1 month after study treatment discontinuation. Male patients willing to abstain or use barrier contraception (i.e. condoms) for the duration of the study and for 3 months after treatment stops.

4.2.2 Concomitant Medications

4.2.2.1 Corticosteroids: Patients receiving corticosteroids are eligible for this trial.

4.2.2.2 Investigational Drugs: Patients who are currently receiving another investigational drug are not eligible.

4.2.2.3 Anti-cancer Agents: Patients who are currently receiving other anti-cancer agents are not eligible.

4.2.2.4 Anticonvulsants: Patients must not currently be receiving enzyme inducing anticonvulsants (see [Appendix II](#) for a list of enzyme inducing and non-enzyme inducing anticonvulsants).

4.2.2.5 Herbal Preparations are not allowed throughout the study. These herbal medications include but are not limited to: St. John's wort, kava, ephedra (ma hung), gingko biloba, dehydroepiandrosterone (DHEA), yohimbe, saw palmetto and

ginseng. Patients should stop using these herbal medications 7 days prior to study enrollment.

4.2.2.6 Any known hypersensitivity or contraindication to the components of the study drug AZD1775.

4.2.3 Infection: Patients who have an uncontrolled infection are not eligible.

4.2.4 Patients who have received a prior solid organ transplantation are not eligible.

4.2.5 Cardiac Disease: Patients with cardiac diseases ongoing or in the past 6 months (e.g. Congestive heart failure, acute myocardial infarction, significant uncontrolled arrhythmias) are not eligible for this trial.

4.2.6 Major surgical procedures \leq 28 days of beginning study treatment, or minor surgical procedures (including VP shunt placement or stereotactic biopsy of the tumor) \leq 7 days. No waiting period required following port-a-cath or other central venous access placement.

4.2.7 Patients who in the opinion of the investigator may not be able to comply with the safety monitoring requirements of the study are not eligible

5.0

TREATMENT PROGRAM

5.1 Overview of Treatment Plan

AZD1775 Administration During Radiation Therapy (Cycle 1)

Treatment	Monday through Friday	Saturday and Sunday
Radiation Therapy	X	
AZD1775 (MK-1775)	X [^]	
Rest Period		X

[^]Frequency of AZD1775 (MK-1775) will vary depending on dose level assignment.

Radiation therapy (XRT) will be given at the current standard dose of 5400 cGy in 30 fractions of 180 cGy Monday through Friday for a total of 30 fractions over 6 weeks, with a rest period on Saturday and Sunday of each week. In the event a radiation fraction is not administered due to a holiday (per institutional schedule) or for another reason (e.g., adverse event, mask re-fitting, etc) it will be made up during week seven (or eight). See [Section 15.0](#) for radiation therapy guidelines.

During radiation, AZD1775 (MK-1775) will be administered orally based on the table above, once each day after that day's radiation therapy fraction, for the duration of radiation treatment

Drug doses should be adjusted based on the BSA calculated from height and

weight measured within 7 days prior to the beginning of chemoradiotherapy course, and according to the dosing nomogram (see [Appendix V-A](#)). See [Appendix V-B](#) for scheduling guidelines based on the day of the week that XRT is initiated. The original dose assignment should be maintained throughout the entire period of radiation therapy.

. If a patient vomits after the dose of AZD1775 (MK-1775) the dose should NOT be repeated.

Note: It is recommended but not required that Day 1 of protocol therapy begin on a Monday. If a fraction of radiation is delayed because of holiday or other logistical reasons (e.g. equipment malfunction), patients should also hold AZD1775 (MK-1775) and only take AZD1775 (MK-1775) on days radiation is given.

Patients should have AZD1775 (MK-1775) prescribed at the beginning of chemotherapy, with detailed instructions about the days of the week that drug is to be administered.

5.2 Criteria for Starting Subsequent Cycles

5.2.1 Chemoradiotherapy

Radiation therapy should not be interrupted for AZD1775-related DLTs unless clinically indicated.

5.3 Dose Escalation Schema

Inter-Patient Escalation The starting dose of AZD1775 (MK-1775) (50 mg/m²; dose level 1) is 40% of the known MTD in adult studies of chemotherapy combination regimens (adult MTD 200 mg which corresponds to 115 mg/m²). If dose level 1 is well tolerated, we will escalate treatment first by increasing the number of days AZD1775 (MK-1775) is given and then by escalating the dose of AZD1775 (MK-1775) stepwise to 95 mg/m² as shown in the table below. If dose level 4 is well tolerated, further dose escalation will be considered after evaluation of the pharmacokinetics and toxicity profile. PK simulation predicts higher exposures in children \leq 6 years of age compared to older children (7 years and above). Therefore the age requirement of the first patient enrolled on dose level 1 will be 7 years or older. PK analysis will be performed prior to opening the study to younger children.

	Day 1-5 Week 1					Day 8-12 Week 2					Day 15-19 Week 3					Day 22-26 Week 4					Day 29-33 Week 5					Day 36-40 Week 6				
Dose Level 1: AZD1775 (MK-1775) 50 mg/m² daily Mon-Fri, alternating weeks (See Appendix V-B if start date not on Monday)																														
XRT	x	x	x	x	x	x	x	x	x	x	x	x	x	x	x	x	x	x	x	x	x	x	x	x	x	x	x			
AZD1775 (MK-)	x	x	x	x	x					x	x	x	x	x				x	x	x	x	x								

1775) 50 mg/m ²																									
Dose Level 2: AZD1775 (MK-1775) 50 mg/m² daily Mon-Fri dosing, alternating with weeks of QOD dosing (See Appendix V-B if start date not on Monday)																									
XRT	X	X	X	X	X	X	X	X	X	X	X	X	X	X	X	X	X	X	X	X	X	X	X	X	
AZD1775 (MK- 1775) 50 mg/m ²																									
Dose Level 3: AZD1775 (MK-1775) 50 mg/m² daily Mon-Fri During Weeks 1-6 (See Appendix V-B if start date not on Monday)																									
XRT	X	X	X	X	X	X	X	X	X	X	X	X	X	X	X	X	X	X	X	X	X	X	X	X	
MK-1775 50 mg/m ²																									
Dose Level 4: AZD1775 (MK-1775) 95 mg/m² daily Mon-Fri During Weeks 1-6 (See Appendix V-B if start date not on Monday)																									
XRT	X	X	X	X	X	X	X	X	X	X	X	X	X	X	X	X	X	X	X	X	X	X	X	X	
AZD1775 (MK- 1775) 95 mg/m ²																									
Dose Level 5: AZD1775 (MK-1775) 130 mg/m² daily Mon-Fri During Weeks 1-6 (See Appendix V-B if start date not on Monday)																									
XRT	X	X	X	X	X	X	X	X	X	X	X	X	X	X	X	X	X	X	X	X	X	X	X	X	
AZD1775 (MK- 1775) 130 mg/m ²																									
Dose Level 6: AZD1775 (MK-1775) 160 mg/m² daily Mon-Fri During Weeks 1-6 (See Appendix V-B if start date not on Monday)																									
XRT	X	X	X	X	X	X	X	X	X	X	X	X	X	X	X	X	X	X	X	X	X	X	X	X	
AZD1775 (MK- 1775) 160 mg/m ²																									
Dose Level 7: AZD1775 (MK-1775) 200 mg/m² daily Mon-Fri During Weeks 1-6 (See Appendix V-B if start date not on Monday)																									
XRT	X	X	X	X	X	X	X	X	X	X	X	X	X	X	X	X	X	X	X	X	X	X	X	X	
AZD1775 (MK- 1775) 200 mg/m ²																									

"X" = treatment; "-" = no treatment

* Further dose escalation will be considered after evaluation of the pharmacokinetics and toxicity profile.

If the MTD has been exceeded at dose level 1, then the subsequent cohort of patients will be treated

at dose level -1 (see below):

Treatment De-Escalation (Dose Level -1)

	Day 1-5 Week 1				Day 8-12 Week 2				Day 15-19 Week 3				Day 22-26 Week 4				Day 29-33 Week 5				Day 36-40 Week 6			
Dose Level -1: AZD1775 (MK-1775) 50 mg/m² QOD alternating weeks See Appendix V-B if start date is not on Monday																								

If dose level -1 is not well tolerated, further de-escalation will not occur. The study will be closed for accrual.

Intra-Patient Escalation

Intra-patient dose escalation is not allowed on this study.

5.4 Grading of Adverse Events

Adverse events (toxicities) will be graded according to the NCI Common Terminology Criteria for Adverse Events (CTCAE) version 5.0. All appropriate treatment areas should have access to a copy of the CTCAE version 5.0. A copy of the CTCAE version 5.0 can be downloaded from the CTEP website (http://ctep.cancer.gov/protocolDevelopment/electronic_applications/ctc.htm).

Any suspected or confirmed dose-limiting toxicity should be reported immediately (within 24 hours) to the Study Chair.

5.5 Definition of Dose-Limiting Toxicity (DLT)

DLT will be defined as any of the following events that are possibly, probably or definitely attributable to AZD1775 (MK-1775). The DLT observation period for the purposes of dose-escalation will be the entire duration of radiation therapy.

Dose limiting hematological and non-hematological toxicities are defined differently.

Interruption of Radiation Therapy

Interruption of planned radiation for 5 consecutive fractions or 10 fractions total due to AZD1775 (MK-1775)-attributable toxicity (and not due to technical issues).

Non-Hematological Dose-Limiting Toxicity

5.5.1.1 Any Grade 3 or Grade 4 non-hematological toxicity attributable to AZD1775 (MK-1775) with the specific exclusion of:

- Grade 3 nausea and vomiting of less < 3 days duration (Grade 3 nausea or vomiting \geq 3 days in the presence of antiemetics will be considered a DLT)
- Grade 3 liver enzyme elevation, including ALT/AST/GGT that returns to levels that meet initial eligibility criteria or baseline

THIS PROTOCOL IS FOR RESEARCH PURPOSES ONLY, SEE PAGE 1 FOR USAGE POLICY

within 7 days. See [Appendix X](#) for values that represent thresholds between CTCAE grades.

Note: For the purposes of this study the ULN for ALT is defined as 45 U/L.

- Grade 3 or 4 fever < 5 days duration.
- Grade 3 infection < 5 days duration.
- Grade 3 hypophosphatemia, hypokalemia, hypocalcemia or hypomagnesemia responsive to oral supplementation
- Any Grade 2 non-hematological toxicity attributable to AZD1775 (MK-1775) that persists for \geq 7 days and is considered sufficiently medically significant or sufficiently intolerable by patients that it requires interruption of AZD1775 (MK-1775) for 7 days.
- Note: Allergic reactions that necessitate discontinuation of study drug will not be considered a dose-limiting toxicity.

Hematological dose limiting toxicity

- Grade 3 thrombocytopenia (platelet count < 50,000/mm³)
- Grade 4 neutropenia

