13.4 Definition of Onset and Resolution of Adverse Events

Note: These guidelines below are for reporting adverse events on the COG case report forms and do not alter the guidelines for CTEP-AERS reporting.

If an adverse event occurs more than once in a course (cycle) of therapy only the most severe grade of the event should be reported.

If an adverse event progresses through several grades during one course of therapy, only the most severe grade should be reported.

The duration of the AE is defined as the duration of the highest (most severe) grade of the Adverse Effects.

The resolution date of the AE is defined as the date at which the AE returns to baseline or less than Grade 1, whichever level is higher (note that the resolution date may therefore be different from the date at which the grade of the AE decreased from its highest grade). If the AE does not return to baseline the resolution date should be recorded as "ongoing."

An adverse event that persists from one course to another should only be reported once unless the grade becomes more severe in a subsequent course. An adverse event which resolves and then recurs during a different course, must be reported each course it recurs.

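### The DLT day limits do not say how repeat episodes are counted, and one-record-per-course reporting loses the number and total days of recurrent Grade 3 or higher events

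*Combined protocol and SAP*

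**What the plan says.** **DLT definition (Section 5.5).** The general rule is "Any Grade 3 or Grade 4 non-hematological toxicity attributable to AZD1775 (MK-1775) with the specific exclusion of", followed by a list. Three exclusions carry a day limit: "Grade 3 nausea and vomiting of less < 3 days duration", "Grade 3 or 4 fever < 5 days duration" and "Grade 3 infection < 5 days duration". The first adds that 3 days or more on antiemetics is a DLT. A fourth, "Grade 3 liver enzyme elevation, including ALT/AST/GGT that returns to levels that meet initial eligibility criteria or baseline", depends on recovery within 7 days. None mentions repeat episodes. The DLT window is the whole of radiation therapy. The same section makes interruption of radiation a DLT at five fractions in a row or ten overall, so there it separates consecutive from total.

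**CRF reporting (Section 13.4).** If an adverse event "occurs more than once in a course (cycle) of therapy only the most severe grade of the event should be reported". On duration: "The duration of the AE is defined as the duration of the highest (most severe) grade of the Adverse Effects". An event that resolves and comes back has to be reported again only when it comes back in a different course.

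**Number of courses.** Section 5.1 heads the treatment table "AZD1775 Administration During Radiation Therapy (Cycle 1"), and Section 10.1 has planned therapy complete on Day 42. No later drug course exists.

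**Use of the data.** Section 11.3 promises a descriptive account of toxicities, with no mention of episode counts or days at grade. It treats the MTD as exceeded at two or more DLTs in a cohort of up to six.

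**The concern.** AZD1775 is given on weekdays with a weekend rest, for up to six weeks, and Section 2.1 expects gastrointestinal effects. Short episodes that return from week to week are a natural pattern to provide for, and the plan leaves two gaps.

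First, two sites could read the same day limit differently and classify the same child differently. That feeds directly into the escalation rule (aim 1.1.1).

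Second, whichever reading is used for DLTs, the CRF rule collapses all episodes of an event into one worst-grade record. A child with one brief Grade 3 episode and a child with six then look alike, or differ only in a duration field whose meaning is not defined. The toxicity description (aim 1.1.2) loses the information that bears most on tolerability of a six-week daily schedule. Both gaps, where they have an effect, make a dose look better tolerated.

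**Working it through.** The plan gives no figure on this point to reproduce. The check sets the rules side by side and counts days.

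**Inputs.** Nausea/vomiting is excluded below 3 days, so at most 2 whole days; fever and infection below 5 days, so at most 4 (Section 5.5). The planned window is 6 weeks, or 42 days (Sections 5.1 and 10.1). Drug is given every week at Dose Levels 2 to 7, and in three alternate weeks at Dose Levels -1 and 1 (Section 5.3, Appendix V-A). There is one course.

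**Step 1: what each rule does with three hypothetical children, all on antiemetics.**

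| Grade 3 vomiting | DLT, days per episode | DLT, days summed over window | CRF record under Section 13.4 |
|---|---|---|---|
| One 2-day episode | No | No | One, Grade 3, 2 days |
| 2 days in each of 6 weeks | No | Yes (12 days) | One, Grade 3; 2 or 12 days, not stated which |
| One unbroken 3-day episode | Yes | Yes | One, Grade 3, 3 days |

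The two readings diverge early. Two 2-day vomiting episodes give 2 + 2 = 4 days, past the 3-day limit if summed. Two 3-day fevers give 3 + 3 = 6, past the 5-day limit if summed. Neither is a DLT per episode. In no row does the CRF hold the number of episodes.

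**Step 2: largest total that stays excluded if each weekly episode is judged alone.**

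- Nausea/vomiting: 6 × 2 = 12 of 42 days (29%).
- Fever or infection: 6 × 4 = 24 of 42 days (57%).
- Dose Levels -1 and 1, counting the three drug weeks only: 3 × 2 = 6 and 3 × 4 = 12 days.

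These are upper bounds, not expectations.

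**Step 3: does the weekend rest alone create an exclusion?** An unbroken Monday-to-Friday episode lasts 5 days. For nausea/vomiting 5 ≥ 3, and for fever or infection 5 is not below 5, so neither is excluded. An episode ending on Friday is excluded only if it began on Thursday or later (nausea/vomiting) or on Tuesday or later (fever, infection).

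**Step 4: how much the reading could matter to escalation.** The documents give no rate for recurrent short episodes, so this is an illustration on assumed values. Suppose 40% of children have unacceptable toxicity, and a share m of them have it only as excluded repeats. The counted rate is q = 0.40 × (1 − m), and in six patients P(at most 1 DLT) = (1 − q)^6 + 6q(1 − q)^5.

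| m | q | P(at most 1 DLT in 6) |
|---|---|---|
| 0 | 0.40 | 0.0467 + 0.1866 = 0.23 |
| 0.25 | 0.30 | 0.1176 + 0.3025 = 0.42 |
| 0.50 | 0.20 | 0.2621 + 0.3932 = 0.66 |

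Approximating the rolling six by escalation on 0 of 3 or 1 of 6, (1 − q)^3 + 3q(1 − q)^5 gives 0.31, 0.49 and 0.71. The direction is fixed by the rules; the size depends wholly on m, which is unknown.

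**The case against.** A reader might infer that recurrent Grade 3 toxicity is exempt from the DLT count and invisible in the results, with the weekend rest as the cause. The documents do not support that.

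- **Visibility.** Section 13.4 requires the worst grade, so the event appears once as Grade 3. Only frequency and total days are lost.
- **Scope.** Outside the exclusion list, attributable Grade 3 or 4 non-hematological toxicity is a DLT at any duration. Grade 3 thrombocytopenia and Grade 4 neutropenia carry no duration condition.
- **Weekend stop.** Step 3 shows that it does not by itself bring an episode under the limits.
- **Per-episode counting.** Section 5.5 is silent. It does not require the 3 days to be consecutive, so a cumulative reading is open.

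There are also safeguards. History and examination are weekly, and diaries with comments go into RAVE weekly (Section 8.1, Appendix IV). Suspected DLTs reach the Study Chair within 24 hours (Section 5.4), and data are reviewed on a weekly call (Section 14.4). Section 13.4 leaves CTEP-AERS reporting unchanged. The separate CRF packet named in Section 14.1 is not available here and may collect more. Experience to the 2016 amendment was benign: 26 patients and one DLT, a Grade 3 ALT rise (Section 2.6).

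All of this limits the point without removing it. The diary records doses and free text, not graded episodes. No review step has a rule for counting repeats. If the CRF packet collects every episode, it departs from Section 13.4 and the two should be aligned.

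**Conclusion.** The point holds as an ambiguity and a data gap. The ambiguity is that Section 5.5 sets day limits without a counting rule for repeats, although it supplies one for radiation interruption. The gap is that, with a single course, Section 13.4 reduces any recurrent event to one worst-grade record, so episode counts and total Grade 3 or higher days are not available to the toxicity summary. The gap follows from the text as written, whichever DLT reading is used.

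That recurrent short episodes escape the DLT count is conditional: it holds only under per-episode counting and only in the categories with a time limit. The bounds are 12 days for nausea/vomiting and 24 for fever or infection over six weeks. Nothing in the documents shows that such patterns occurred, and the probabilities in Step 4 rest on an assumed 40% rate and assumed shares. This is a low-cost improvement to a primary aim, not evidence that any dose level was misjudged.

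**What to change.** 1. **Section 13.4:** for the DLT window, replace the single worst-grade record with one entry per Grade 3 or higher episode, with start and stop dates. The existing rule can stay for lower grades.
2. **Section 11.3:** add to the descriptive toxicity summary the number of Grade 3 or higher episodes and the total days at Grade 3 or higher, per patient, by dose level.
3. **Section 5.5:** the sponsor should state how repeat episodes count toward the existing day limits and toward the 7-day liver enzyme recovery. Which rule to adopt is a clinical choice for the sponsor. Once it is stated, all sites classify alike, and the dated entries let the summary be read either way.

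The cost is a few extra CRF lines per affected patient, a sentence in each of Sections 5.5 and 11.3, and a check that the CRF packet agrees with Section 13.4. If the sponsor chose to sum days, some children not counted under per-episode reading would become DLTs. That would also trigger the dose-modification provisions of Section 6.2, so it needs to be weighed when the rule is chosen.
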